## **Behavioral data analysis for neurostimulation experiments:**

The effect of anodal (excitatory), cathodal (inhibitory) or sham tDCS stimulation on the prevalence of model-based (MB) and model-free (MF) action selection (number of trials in which MB or MF strategy could be used for action selection) and their ratio could be tested during the decision-making task performance. ANOVA and linear mixed-effects model could be applied, respectively, to compare the effect of different stimulation conditions (anodal, cathodal and sham) on behavioral performance and to compare the effect of two active stimulations (anodal, cathodal) as separate condition factors against sham, while controlling for the time factor between baseline (imaging with no tDCS) and tDCS sessions and treating participants as random effects. For symptom provocation-avoidance task, the effect of anodal, cathodal or sham tDCS stimulation could be evaluated on the timing of avoidance behavior (the duration of time that participants tolerate the OCD-relevant or aversive pictures before pushing the stop button).

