## **Objective**

The objective of this project was to explore the neurobehavioral characteristics of an arbitration mechanism, which has been demonstrated to regulate contributions of goal-directed and habitual strategies of action selection in non-clinical populations, in OCD.

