## **Design**

We recruited 30 male and female adults (age 18-65) with OCD and 30 age-, sex-, and education-matched healthy (medically, neurologically and psychiatrically) controls for this project. Each participant came for three sessions. There were 3-8 days interval between sessions:

Session 1 that included initial clinical assessment and obtaining T1 structural image.

Session 2 and 3 that included performing two separate decision-making and symptom provocation-avoidance tasks (see below for more information) by participants with OCD and healthy controls under two conditions: while scanned inside the MRI scanner (no tDCS) or while receiving tDCS neurostimulation outside the scanner (no fMRI imaging). As participants performed each task twice, there might be an order effect on task performance. For minimizing the impact of such a potential order effect on imaging and tDCS results, participants were randomly assigned to undergo scanning in the session 2 and then receive tDCS in the session 3

or in the opposite order (tDCS in session 2 and then imaging in session 3) but in each session only one of imaging or tDCS experiments (for both tasks) could be conducted for each participant.

OCD-relevant and aversive picture rating (explained below) could be done always in the session 3 as the last experiment.

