### **Methods:**

We examined the activity and connectivity patterns of the arbitration regions that have been previously determined to comprise the right and left inferior lateral prefrontal cortex (ilPFC) and right frontopolar cortex (FPC) in individuals with OCD. We acquired functional magnetic resonance imaging (fMRI) data while participants performed a decision-making (DM) task in which goal-directed and habitual action selection strategies compete to govern behavior control. Furthermore, we tested activity and network connectivity of the arbitration regions during the performance of a more clinically relevant symptom provocation-avoidance (SP-A) task. To additionally probe this mechanism, we used the non-invasive brain stimulation method of transcranial Direct Current Stimulation (tDCS). Excitatory and inhibitory currents applied by tDCS over a targeted arbitration region, the left ilPFC, while participants performed the DM and SP-A tasks to further corroborate whether the target arbitrator has causal effects on task performance and habitual/goal-directed action selection balance.

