### **Statistical analysis plan:**

For this study we assumed a data loss of about 10% leading to a final usable data sample size of  $n=30$  OCD participants and 30 age-, sex, and education matched healthy controls for a final sample size of  $n=60$ . This sample size could provide sufficient power ( $>.8$ ) to detect group differences of  $d=.73$ , and associations between continuous variables as small as  $r=.35$ . For regression analyses within the OCD sample, we are able to detect associations as small as  $r=.48$  reliably (power $>.8$ ). In Gillan et al, 2015 study (fMRI imaging of avoidance decision-making in OCD), the differences in the BOLD signal in the medial orbitofrontal cortex during acquisition of avoidance between OCD and controls showed effect sizes of  $d=1.23$ , and during overtraining of avoidance effect sizes of 1.19. Association between behavioral measures (urge to respond) and activity in the caudate showed an effect size of  $r=.63$ . The proposed study provides a power of  $>.99$  for effects of this size, and based on this we consider this study to be sufficiently powered for the fMRI aims. Effect sizes in Gillan et al., 2011 study, for the association between a behavioral measure comparable to the paradigm proposed here and OCD symptom severity is  $r=.56$ , an effect size that can be reliably (power=.91) detected in the OCD sample in this study ( $n=30$ ). In a comparable tDCS/decision making study (Weissengruber et al. 2020), showed the behavioral effects of cathodal stimulation with effect sizes of  $d=.77$  for model-free action selection, and  $d=.65$  for reduction of switching. The proposed sample size provides power of .97 and .92 respectively to detect effects of this size. Based on these studies with comparable experimental design, we consider the proposed project to be sufficiently powered to detect the OCD related group differences in both behavioral and imaging data, association between behavioral and imaging data, and effects of tDCS on behavioral performance in an instrumental decision-making experimental paradigm.

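### As written, the tDCS models have no diagnosis term, no diagnosis-by-stimulation interaction and no OCD-specific contrast, although both groups are stimulated and the objective concerns OCD

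*Combined protocol and SAP*

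**What the plan says.** All references are to the combined protocol and SAP.

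- **Objective.** "The objective of this project was to explore the neurobehavioral characteristics of an arbitration mechanism". The section treats this mechanism as already shown in people without the disorder; the open question is OCD.
- **Design.** "We recruited 30 male and female adults (age 18-65) with OCD and 30 age-, sex-, and education-matched healthy" controls. Both tasks are done "by participants with OCD and healthy controls under two conditions", one in the scanner and one with tDCS, so both groups are stimulated. The section adds: "As participants performed each task twice, there might be an order effect on task performance".
- **Methods.** Stimulation of the left ilPFC is meant "to further corroborate whether the target arbitrator has causal effects on task performance and habitual/goal-directed action selection balance". No population is named.
- **Behavioral data analysis for neurostimulation experiments.** An ANOVA compares anodal, cathodal and sham. A mixed model serves "to compare the effect of two active stimulations (anodal, cathodal) as separate condition factors against sham", adjusting for time between the baseline and tDCS sessions, with participant as a random effect. For the symptom provocation-avoidance task, the stimulation effect on avoidance timing is to be evaluated, with no model terms given. Diagnosis is not mentioned for either task.
- **Imaging (fMRI) data analysis.** Here, by contrast, group-level comparisons are named.
- **Statistical analysis plan.** Power of .97 and .92 is stated for cathodal effects of d = .77 and d = .65.

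**The concern.** The issue is whose stimulation effect is estimated. It is not a matter of adding diagnosis as a covariate to gain precision. A model holding only stimulation, session and participant returns one coefficient per active condition, averaged over the two diagnoses. If the arbitrator behaves differently in OCD, as the study supposes it may, that average tells us neither whether stimulation acts in OCD nor whether its effect differs from that in controls.

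Two things could go wrong. A positive average could be produced entirely by controls, repeating what the Objective already treats as established, and still be read as causal evidence about OCD. An effect confined to OCD would be diluted. Leaving diagnosis open also allows the choice among pooled, stratified and interaction models to be made after the results are seen.

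**Working it through.** **Inputs from the document.** 30 OCD and 30 controls; both groups stimulated; d = .77 and .65; stated power .97 and .92.

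**Assumptions, because the document is silent.** Two-sided alpha .05. Stimulation is either between people (equal allocation, 30/3 = 10 per arm per diagnosis, tDCS-session outcome only) or within people (30 per diagnosis). Each d is standardized on the scale of the contrast tested, with unit SD within diagnosis.

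**Step 1: the plan's own figure.** Power comes from the noncentral t distribution. For a paired test the noncentrality is d√n with n − 1 degrees of freedom; for two equal groups of n it is d√(n/2) with 2n − 2.

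| Calculation | d = .77 | d = .65 |
|---|---|---|
| Stated in the plan | .97 | .92 |
| Paired, n = 30 | .983 | .931 |
| Paired, n = 60 | 1.000 | .999 |
| Two-sample, 30 v 30 | .835 | .697 |
| Two-sample, 20 v 20 | .660 | .517 |

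The nearest match is a within-person contrast in 30 people, the size of one group. It is approximate.

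**Step 2: dilution.** With equal groups, the averaged effect is (30 × d + 30 × 0)/60 = d/2. So .77 becomes .385, and .65 becomes .325.

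**Step 3: rejection by the averaged test when the effect is in one group only.** The result is the same whichever group has the effect.

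- Within-person, n = 60: noncentrality .385 × √60 = 2.98, power .83. With no diagnosis term, the group difference inflates the SD to √(1 + .77²/4) = 1.072, so the standardized effect is .385/1.072 = .359 and power is .78. Simulating the two-group mixture gives .80. For d = .65 the analytic range is .65 to .70.
- Between-person, 20 v 20: noncentrality .385 × √10 = 1.22, power .22, or .20 with the inflated SD and in simulation. For d = .65 it is .16 to .17.

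**Step 4: the OCD-only contrast.**

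- Within-person, n = 30: .98 (d = .77) and .93 (d = .65).
- Between-person, 10 v 10: noncentrality .77 × √5 = 1.72, power .37; for d = .65, .28.
- 95% CI half-width: within-person 2.045/√30 = .37 SD; between-person 2.101 × √(2/10) = .94 SD.

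**Step 5: diagnosis-by-stimulation interaction, full effect in one group and none in the other.**

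- Within-person, 30 v 30 differences: .83 and .70.
- Between-person, four cells of 10: noncentrality .77/√(4/10) = 1.22, power .22; for d = .65, .17.

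**Summary for d = .77 in one group only**

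| Test | Between-person | Within-person |
|---|---|---|
| Averaged over both groups | .20 to .22 | about .80 |
| OCD-only, effect in OCD | .37 | .98 |
| Interaction | about .22 | .83 |

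**The case against.** A reader might infer that the plan pools the groups and never estimates the effect in OCD. The document does not support that. No sentence prescribes pooling, and none prescribes analysis by group. The stated power lies near a within-person calculation with n = 30, which fits analysis by group at least as well as pooling. This is only weak evidence: the match is inexact, and the power section says explicitly when it means the OCD sample, whereas for tDCS it refers only to the proposed sample size. That section also expects OCD-related group differences in behavioral data, but lists tDCS effects separately, so it does not supply the missing interaction.

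The Methods aim for tDCS names no population, and an averaged effect is a legitimate answer to it. The rejection rates for a controls-only effect are therefore not false-positive rates, because the average effect really is non-zero. Harm arises only if the average is then reported as an OCD finding.

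The between-person figures come from post-only t-tests, not the planned mixed model. Using baseline moves them. With 10 per cell and d = .77, change scores give OCD-only power .56 and averaged power .33 at a baseline-outcome correlation of .7, and .28 and .17 at .3. They indicate size and do not forecast the planned model's power. Two runs of each task, one with tDCS, make between-person stimulation plausible, while the stated power points the other way, so neither design can be shown alone.

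What survives all this is the omission: no other section says how diagnosis enters the tDCS analysis.

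**Conclusion.** The point holds as an unspecified estimand with conditional consequences. If the model is fitted with only its named terms, a one-group effect of .77 is halved to about .385, and the averaged test cannot show which group produced it.

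The two designs fail differently. Between people, the averaged test has little power for an OCD-only effect (.20 to .22, against .37 for the OCD contrast). Within people, it would be significant about 80% of the time for an effect wholly in controls, while the unplanned OCD contrast would have had power .98. Misattribution is then the larger risk, and precision is no reason to omit the contrast.

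These sizes rest on two-sided .05, equal allocation in the between-person case, and the plan's d values applying to the contrast tested. The omission does not depend on any of them. It should be corrected, but it does not invalidate the study.

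**What to change.** In the neurostimulation analysis section:

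1. Add diagnosis and diagnosis × stimulation to the models, and diagnosis × session × stimulation to the two-session model.
2. Report each active-versus-sham effect with a 95% confidence interval in OCD, which answers the Objective, and in controls. Do this for the MB and MF measures, their ratio, and avoidance timing.
3. Label any pooled effect as an average over both groups, and do not rest a statement about OCD on it alone.
4. State whether each participant received one or all of the stimulation conditions, since this determines the precision. If separate analyses by group were always intended, say so.

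The cost is SAP wording and a few model terms, with no new data. The drawback is that, if stimulation is between-person, the OCD-specific intervals will be wide (about ±.94 SD on the post-only calculation) and the interaction test weak. Both should be described as such; a non-significant interaction would not show that the groups respond alike.

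### The three-condition tDCS ANOVA leaves out each participant's no-tDCS score, and neither tDCS analysis names session order: an avoidable loss of precision

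*Combined protocol and SAP*

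**What the plan says.** All references are to the combined protocol and SAP.

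*Behavioral data analysis for neurostimulation experiments* names two methods: "ANOVA and linear mixed-effects model could be applied, respectively". The ANOVA serves "to compare the effect of different stimulation conditions (anodal, cathodal and sham) on behavioral performance". The mixed model enters anodal and cathodal stimulation "as separate condition factors against sham, while controlling for the time factor between baseline (imaging with no tDCS) and tDCS sessions", "treating participants as random effects". Because the methods and purposes are paired, the adjustment for the no-tDCS session attaches to the mixed model and not to the ANOVA. No model equation is given. A condition-by-session term is neither named nor excluded, and the value that condition takes in the no-tDCS session is not stated. For the symptom provocation-avoidance task, the section names an outcome (avoidance timing) but no model.

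*Design* explains the two sessions: "As participants performed each task twice, there might be an order effect on task performance". Order is therefore randomised, either imaging first "or in the opposite order (tDCS in session 2 and then imaging in session 3"). It adds that "in each session only one of imaging or tDCS experiments (for both tasks) could be conducted for each participant". The documents do not say how many stimulation conditions a participant receives, how many participants receive each, or how they are assigned.

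**The concern.** Each task is done once without stimulation and once with it. The likely reading is that each participant has one stimulation condition, so active versus sham is a comparison between people, and the no-tDCS score is a measure of the same person on the same task. An ANOVA of the tDCS session alone leaves between-person variation in its error term when the data to remove it are already collected.

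Order is a separate gap. The time factor in the mixed model is session type (imaging or tDCS). Because order is randomised, session type is not session number, so this factor does not absorb a practice or fatigue effect from session 2 to session 3. The design anticipates such an effect, yet no analysis term is named for it.

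The comparison matters because *Methods* relies on it to show whether the left ilPFC has a causal role in the balance of action selection.

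**Working it through.** **Inputs from the documents.** 60 usable participants (30 OCD, 30 controls); cited tDCS effects d = .77 and .65; stated power .97 and .92 (*Statistical analysis plan*).

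**Assumptions, none given in the documents.** One condition per participant; 60/3 = 20 per condition; correlation ρ between the two sessions .3 to .7; two-sided alpha .05; within-group SD 1; the cited d treated as a shift of one arm in the tDCS session.

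**1. The plan's own power figures.** A one-sample or paired t-test with n = 30 gives .983 and .931, the closest match to .97 and .92. A two-sample test of 30 v 30 gives .835 and .697; 20 v 20 gives .660 and .517. The stated figures thus resemble a within-person test, and they do not describe the three-condition ANOVA.

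**2. ANOVA without the no-tDCS score.** With one of three arms shifted by d, the noncentrality is λ = 20 × d² × 2/3.
- d = .77: λ = 20 × .5929 × 2/3 = 7.91; F(2, 57) gives power .69 (.67 to .70 by simulation).
- d = .65: λ = 20 × .4225 × 2/3 = 5.63; power .53.

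**3. Adding the no-tDCS score as covariate.** Residual variance falls to 1 − ρ², so λ becomes λ/(1 − ρ²), with F(2, 56).

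| ρ | λ, d = .77 | power | λ, d = .65 | power |
|---|---|---|---|---|
| .3 | 7.91/.91 = 8.69 | .73 | 5.63/.91 = 6.19 | .57 |
| .5 | 7.91/.75 = 10.54 | .81 | 5.63/.75 = 7.51 | .66 |
| .7 | 7.91/.51 = 15.50 | .94 | 5.63/.51 = 11.05 | .83 |

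Simulation for d = .77 gives .71 to .93. It runs slightly lower because the formula ignores chance imbalance in the covariate.

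**4. Session order.** Assume equal allocation to the two orders and a shift of .5 SD from session 2 to session 3.
- Unadjusted, the shift adds .5² × ¼ = .0625 to the variance: λ = 7.91/1.0625 = 7.44, power about .66 (about .65 by simulation).
- Order moves a participant's two scores in opposite directions, so ignoring it also weakens the covariate. The working correlation becomes (ρ − .0625)/1.0625 = .22, .41 and .60 for ρ = .3, .5 and .7. Then λ = 7.44/(1 − r²) = 7.83, 8.96 and 11.63, with power about .68, .74 and .85.
- With both score and order in the model, simulated power is .72 to .93.

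**5. Coding of condition in the mixed model (true effect .77).**
- Condition as a participant label in both sessions, no interaction: the coefficient averages the sessions, (0 + .77)/2 = .385. The participant mean has variance (1 + ρ)/2, so the standardised effect is .385/√((1 + ρ)/2) = .48 to .42, and power at 20 v 20 is .31 to .25.
- Indicators on only in the tDCS session, main effects only: simulated coefficient .78 to .80, so not halved.
- Condition-by-session interaction with a condition main effect also fitted: full effect (.77 to .79), with change-score power of .52 to .87.
- tDCS session alone, as in the ANOVA: .79 to .82, full effect.

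These simulated coefficients carry Monte Carlo error of about .02 to .03.

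**The case against.** A reader might infer that the mixed model has main effects only and therefore estimates half the true effect. The documents do not support that. They give no equation, and halving needs an unstimulated imaging session to be labelled anodal or cathodal. The section calls that session a baseline, which fits indicators switched on only under stimulation at least as well. Under that coding, simulated power for d = .77 is .71, .79 and .92 at ρ = .3, .5 and .7, about the same as covariate adjustment. This objection stands: halving is a possible result of unclear wording, and not a property of the plan.

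It can also be said that the ANOVA is unbiased under random assignment and that the mixed model already uses the no-tDCS session, so the measure is not thrown away. Both are right. The ANOVA remains the named method for comparing the three conditions, however, and its loss of precision is avoidable. At ρ = .3 the gain is small. If anodal and cathodal shift in opposite directions by .77 each, omnibus power is already .99 and the gain there is negligible.

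Lastly, a between-person condition is inferred. Two performances per task, one of them in the scanner, make it likely, but no text says so, and the stated powers look like a within-person test. If each participant received several conditions, the figures above would not apply. The missing order term would remain.

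**Conclusion.** The point holds as a matter of precision and specification. The ANOVA as described makes no use of the no-tDCS score, and no analysis names session order although the design randomises it for a stated reason. On the listed assumptions, adding the score raises omnibus power for one arm shifted by .77 from about .67 to .70 up to .71 to .93. With an assumed order effect of .5 SD, the comparison is about .65 with no adjustment against .72 to .93 with score and order. The size depends mainly on the session correlation, which the documents do not give.

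This is not bias if conditions are randomised, but assignment is not described. The mixed model uses the no-tDCS session, and its coding there needs to be stated. Only a participant-level label in both sessions without an interaction would turn .77 into .385.

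**What to change.** For each behavioural outcome, including avoidance timing, write one model equation: the tDCS-session value as response, with condition (anodal, cathodal, sham), the no-tDCS-session value, diagnosis and session order. Take the omnibus test and both active-versus-sham contrasts from it, and drop the separate ANOVA.

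A mixed model on both sessions is an acceptable alternative if the tested term is condition-by-session, written as condition indicators active only in the tDCS session, plus session type, session number (2 or 3), diagnosis and a random participant intercept. Leave out a separate condition main effect, since adding one turns the test into a change-score comparison with the lower power shown above.

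Report order-by-condition as a sensitivity analysis. For some participants the no-tDCS session comes 3 to 8 days after stimulation, so that score is a clean covariate only if nothing carries over. State also how many conditions each participant receives and how they are assigned.

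Cost: SAP wording and a few degrees of freedom. No new data are needed.

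### Session order is randomised because of a possible practice effect, but the tDCS models do not clearly adjust for session 2 versus session 3

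*Combined protocol and SAP*

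**What the plan says.** The Design section warns: "As participants performed each task twice, there might be an order effect on task performance". It randomises participants to imaging then tDCS, or the reverse, and gives this purpose: "For minimizing the impact of such a potential order effect on imaging and tDCS results". It adds that "in each session only one of imaging or tDCS experiments (for both tasks) could be conducted for each participant", so each participant has one tDCS session and one imaging session. On spacing it says: "There were 3-8 days interval between sessions".

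The section on behavioral data analysis for neurostimulation names an ANOVA across anodal, cathodal and sham, and a linear mixed-effects model comparing each active condition with sham, "while controlling for the time factor between baseline (imaging with no tDCS) and tDCS sessions and treating participants as random effects". For the symptom provocation-avoidance task it says only that "the effect of anodal, cathodal or sham tDCS stimulation could be evaluated on the timing of avoidance behavior", with no model or covariate. Neither session number nor randomised order is named as a model term anywhere.

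**The concern.** Session type (imaging or tDCS) and chronological session (2 or 3) are different variables here, because order is randomised. A term for one does not adjust for the other. The scan is called baseline, yet in the tDCS-first sequence it comes after stimulation, so the time factor cannot literally be session 2 versus 3.

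If performance shifts between the two runs of a task, the tDCS-minus-imaging change carries that shift with a plus sign in one sequence and a minus sign in the other. Without a term for it, the shift becomes residual noise. The comparison affected is the one the Methods section relies on "to further corroborate whether the target arbitrator has causal effects on task performance and habitual/goal-directed action selection balance". If each participant received one stimulation condition, it is made between small arms. The design randomised this factor; the analysis should use it.

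**Working it through.** **The plan's own figure.** The statistical analysis plan gives tDCS power of .97 for d=.77 and .92 for d=.65. With a two-sided 5% test (assumed; no alpha is stated), a paired comparison of 30 has noncentrality d√30, that is 4.22 and 3.56, and power .983 and .931, within 2 points of the plan. A comparison of 30 with 30 gives .835 and .697; 20 with 20 gives .660 and .517. So the stated power matches a within-person contrast. It does not bear on the order question, but it shows that the basis of the tDCS comparison is not settled.

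**Inputs.** From the documents: 60 participants, three conditions, two sessions, d=.77. Assumed: one condition per participant, 20 per condition, single-session SD 1, between-session correlation ρ=.6, and a practice shift δ from session 2 to session 3 of 0 to 0.8 SD.

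**Formula.** Code the shift as −δ/2 in session 2 and +δ/2 in session 3. With order split evenly and not modelled:
- variance of each score: V = 1 + δ²/4
- covariance of the imaging and tDCS scores: C = ρ − δ²/4
- residual variance of the tDCS score given the imaging score: R = V − C²/V
- 95% half-width for one active condition against sham: about 2.00 × √(2R/20)

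With session modelled, V=1, C=.6 and R = 1 − .36 = .64, so the half-width is 2.00 × √.064 = .51 (simulated .50).

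The power columns come from simulation (3,000 replicates per setting, REML compound-symmetry model, order 10/10 within condition).

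| δ (SD) | V | C | R | Half-width without term: formula | Simulated | Power without | Power with session 2/3 |
|---|---|---|---|---|---|---|---|
| 0 | 1 | .6 | .640 | .51 | – | .855 | .855 |
| 0.3 | 1.0225 | .5775 | .696 | .53 | .53 | .822 | .850 |
| 0.5 | 1.0625 | .5375 | .791 | .56 | .56 | .785 | .843 |
| 0.8 | 1.16 | .44 | .993 | .63 | .63 | .691 | .846 |

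**Sensitivity to the assumptions** (power without → with, at 0.3 / 0.5 / 0.8 SD):
- ρ=.4: .731→.748, .704→.748, .641→.745
- ρ=.8: .967→.981, .939→.980, .809→.980
- order 30/30 overall but not balanced within condition: .818→.844, .778→.853, .652→.840
- tDCS-session scores alone, adding order: .652→.663, .643→.668, .606→.660

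**A main effect of order does not help the two-session model.** It shifts both of a participant's scores equally. Simulated power with it is .854, .822, .784 and .691 at 0, 0.3, 0.5 and 0.8 SD, essentially the same as with no term.

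**Type I error at 0.8 SD.** Without the term it is .018 if order is balanced within condition and .056 if not; with the term, .050 and .049.

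**Chance imbalance.** The documents do not say that order is balanced within condition. Suppose 13 of 20 cathodal and 7 of 20 sham participants are imaging-first, a difference of .30. The tDCS means then differ by .30δ and the imaging means by −.30δ, so the unadjusted estimate moves by .30δ(1 + C/V):
- 0.3 SD: .09 × 1.565 = .14, giving .91
- 0.5 SD: .15 × 1.506 = .23, giving 1.00
- 0.8 SD: .24 × 1.379 = .33, giving 1.10

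The mirror-image split lowers the estimate to .63, .54 and .44. With the session term it stays at .77 to .78. About 8% of unstratified allocations are at least this uneven between two given arms.

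**The case against.** The strongest reply is that this is a query about one undefined phrase. If the authors meant session 2 versus 3, or a signed elapsed time, the mixed model already handles practice. Randomised order already prevents systematic bias, and the type I errors above show no serious threat to validity. The plan says only that an order effect is possible. At 0.3 SD the gain is 1 to 3 points across the variants shown; the 16-point gain needs 0.8 SD, which nothing in the documents supports. The uneven split is a tail case, and its expected bias is zero. One condition per participant is an inference. If all conditions were run within a single tDCS session, session order would largely cancel from their contrast.

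Much of this stands. The loss is of precision, it may be small, and the sizes rest on assumptions. It does not remove the point: calling the scan baseline fits session type better than session number, the text needs correcting under either reading, and the ANOVA and avoidance-timing analyses name no time or order adjustment that can be clearly attributed to them.

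**Conclusion.** The concern holds. As worded, the tDCS models do not clearly adjust for the order effect that the design was randomised to handle. The consequence is wider intervals and exposure to chance imbalance, not systematic bias. Under the stated assumptions with order balanced within condition, the mixed model loses about 3, 6 and 16 points of power at practice effects of 0.3, 0.5 and 0.8 SD, and nothing at zero. Analyses of tDCS-session scores alone lose much less, about 1 to 5 points. The practice effect, correlation, arm sizes and single condition per participant are all assumed. The change is worth making because it costs almost nothing.

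**What to change.** 1. Define the time factor. In the two-session mixed model, include chronological session (2 versus 3) as a term separate from session type. If that was already the intention, say so.
2. In analyses with one score per participant (the ANOVA, if run that way, and avoidance timing), include randomised order.
3. State how many stimulation conditions each participant received, and whether participants with OCD and controls are pooled.

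The cost is about one degree of freedom, using data known for every participant. With no practice effect, power is .855 with or without the term if order is balanced within condition, and .852 against .855 if it is not.

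Optional: in tDCS-first participants the no-stimulation score follows tDCS by 3–8 days, so a sensitivity analysis could omit it and regress the tDCS-session score on stimulation, order and diagnosis. If 25% or 50% of a .77 effect persisted (assumed), the mixed model with session would estimate about .71 or .66; the sensitivity model would stay near .77. Its power is only about .67, so it should support the main analysis and not replace it.
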